1.2. Investigational Medicinal Product Name

1.2.1. General Information

For further information on NB01, refer to the current investigator's brochure (IB) for NB01.

1.2.2. Preclinical Pharmacology and Toxicology

There is no animal *in vivo* data to date on the safety or clinical efficacy of a topical live *P. acnes* microbiome transplant. There are no well substantiated animal models for inflammatory acne and Naked Biome is investigating human-specific bacteria. Therefore, *in vivo* animal clinical and toxicology studies will not yield clinically relevant results that would be applicable for human use. Animal clinical and toxicology studies are not relevant or useful when using human-specific bacteria absent well-substantiated animal models for inflammatory acne for pre-human efficacy testing (Mirshahpanah and Maibach 2007). The best, most relevant, and only useful model to test NB01 is first in humans

([Mirshahpanah P, Howard Maibach 2007](#); [Achermann et al. 2014](#)). Additional literature on previous human studies for probiotics and acne are referenced ([Baquerizo et al. 2014](#); [Wei et al. 2016](#); [Thiboutot et al. 2009](#)).

1.2.3. Clinical Studies of NB01

The first clinical study of NB01, NB01-P1BSA, is a Phase Ib single-center open-label dose-escalation study using a single dose application with monitoring over 28 days on 10 subjects at two different concentrations (lower bound (10^4 CFU/cm²) and upper bound (10^5 CFU/cm²)). This study is ongoing, however, in meeting the safety criteria of this initial study, Naked Biome plans to expand the IND research to a Phase Ib multi-dosed study under this protocol. All subjects will have been pre-treated with a daily 5.0% BPO gel (Perrigo 5% Benzoyl Peroxide Aqueous Gel) to decrease their resident microbiome bacterial load in preparation for transplantation and successful repopulation with a healthy microbiome.

1.3. Rationale for This Study

Acne vulgaris is a multifactorial disease affecting 85% of the global population over a lifetime and 40-50 million people in the US currently. It impacts individuals over a large timespan ranging from 13-40 years and has a large psychosocial impact on an individual's self-esteem. The majority of those afflicted (50%-75%) are now resistant to conventional antibiotic therapy ([Walsh et al. 2016](#)). Acne is caused by overgrowth of *P. acnes*, impaction of hair follicles, excessive sebum production and hormonal dysregulation. Current standard of care includes treatment with 5.0% BPO, retinoids, and antibiotics. However, there are significant side effects of the above medications, limiting subject compliance and leading to suboptimal long-term efficacy. The heavy dependence on long treatment courses of antibiotics combined with antibiotic resistance rising upwards of 50%-75%, is resulting in treatment failures and contributing to overall global antibiotic resistance. There has been little innovation in acne therapy in the past several decades and a significant current need to develop antibiotic alternatives.

Current therapeutic options include:

- Topical antibiotics-erythromycin/clindamycin
- Oral Antibiotics-tetracycline, doxycycline, minocycline
- Topical 5.0% BPO products
- Topical retinoids
- Oral Retinoids
- Topical acids-salicylic acid, glycolic acid
- Peels
- Blue and red-light therapies
- Dapsone (Aczone®)
- Azelaic acid (Finacea®)

Recent literature from the Human Microbiome Project has shown there are unique microbial signatures specific to healthy and acne disease states ([Fitz-Gibbon et al. 2013](#); [Tomida et al.](#)

2013). Subsequent literature discovered a repressor in the porphyrin pathway in health-associated strains resulting in significantly lower porphyrin production (Johnson et al. 2016). Porphyrin is a known inflammatory mediator in acne pathogenesis (Kang et al. 2015). Porphyrin levels inversely correlate with therapeutic improvement in acne (Richter et al. 2016). Additional papers have highlighted other virulent factors such as the pIMPLE plasmid that may be associated with acne pathogenesis and were found to be more common in disease-associated strains (Kasimatis et al. 2013).

From this data, the Sponsor believes that by eliminating resident disease-associated bacterial strains and replacing them with a health-associated *P. acnes* transplant, there is the potential to improve, mitigate, treat, or prevent acne flares. Naked Biome is currently testing this in an initial Phase I study evaluating the safety, tolerability, and clinical impact that a single dose application of NB01 has on adult subjects with moderate acne. Naked Biome aims to test this further in multiple dosing with NB01 on subjects under this protocol.

1.4. Risk/Benefit Assessment for the Study

The risks of this study are that the applied study drug may contribute to worsening of disease and/or subjects may experience side effects including but not limited to unlikely opportunistic infections, irritation, dryness, or redness. The benefits are that individual subjects may have improvement of their disease. Overall benefits to society include development of novel therapeutics for the treatment of acne.

1.5. Compliance

This study will be conducted in compliance with this protocol, Good Clinical Practice, and all applicable regulatory requirements.

2. OBJECTIVES

The objectives of this study are:

1. Primary: To determine the safety and tolerability of a multiple application of topical *P. acnes* microbiome transplant ("NB01").
2. Exploratory:
 1. To define engraftment duration of NB01.
 2. To evaluate preliminary clinical efficacy using Acne Lesion Counts (total, inflammatory, and non-inflammatory), IGA, and subjective improvement of acne based on subject reported outcomes (Acne QoL Questionnaire).
 3. To evaluate treatment effects, based on sebum production in a subpopulation from sites 02 and 03.

3. STUDY DESIGN

3.1. Study Measurements

3.1.1. Dosing Compliance

Measures of study drug compliance will include the duration (days) of treatment (defined as last dose date – first dose date +1), the total number of applications (determined from the doses reported in the Subject Diary), and the percent of expected doses applied. Subjects who apply at least 80% of the expected total number of applications and have no other evidence of material dosing non-compliance will be considered to be compliant with study drug dosing.

3.1.2. Primary Safety

Adverse Events

All reported or observed AEs will be recorded. At each visit, subjects will also be questioned specifically about the status of any ongoing AEs. Untoward events that occur prior to the first dose of study drug will be captured in the medical history section of the electronic case report form (eCRF) unless they are related to a study-specific procedure.

Local Skin Reactions

At each visit, LSRs will be assessed. Erythema, edema, erosion/ulceration, scaling/dryness, and scabbing/crusting in the treatment area will be assessed by the PI and itching and pain in the treatment area will be assessed by the subject using a 4-point ordinal scale where 0=absent, 1=mild (slight, barely perceptible), 2=moderate (distinct presence), and 3=severe (marked, intense). Only LSRs that require medical intervention (e.g., prescription medication), require withholding or discontinuation of the application of the study drug, or extend 2 cm beyond the treatment area will be documented as AEs. Any LSRs that are not listed above will be recorded as an AE.

LSRs will also be assessed by subjects weekly during the Screening, Treatment and Follow-up periods using a subject diary to assess redness, swelling, erosion/ulceration, scaling/dryness, scabbing/crusting, itching and pain by the same 4-point scale used during clinic visits. Subjects will be asked to record the greatest severity of each LSR experienced during the previous 7 days.

Limited Physical Examination

The limited physical examination will include examination of the face, chest, arms, and back (i.e., relevant acne regions) Abnormalities at Screening/Baseline will be recorded as medical history. Any new or worsening abnormalities at Visit 5/EOT will be recorded as AEs.

Vital Signs

Vital signs including blood pressure, heart rate, and temperature will be measured at Screening/Baseline and Visit 5/EOT. Assessments will be made after the subject has rested in a seated position for at least five minutes.

Complete Blood Count

CBC will be assessed locally at Screening and Visit 5/EOT and must include Differential.

Urine Pregnancy Test

A UPT will be performed at Screening/Baseline and Visit 5/EOT for WOCBP.

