7.2.3. Clinical Laboratory Abnormalities and Other Abnormal Assessments as Adverse Events or Serious Adverse Events

The PI will evaluate clinical laboratory results, physical exam findings and vital signs to determine if any findings are clinically significant. Any clinically significant results that represent and new or worsening change from Baseline should be recorded as an AE.

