8.12.4 Physical Examination

Findings from the physical exam will be recorded in medical history (from assessment at Screening and Baseline) or as AEs (from assessment at Visit 5/EOT).

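### A listed skin reaction on the face that is new or worse at the Visit 5 examination is an AE under one sentence of Protocol 3.1.2 and, without a trigger, not under another, so overall AE incidence depends on which sentence a site follows

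*Protocol*

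**What the plan says.** **Examination rule.** Protocol 3.1.2 states: "The limited physical examination will include examination of the face, chest, arms, and back". The face is the treatment area (Protocol 4.3, exclusion 6). The rule for what is found is "Any new or worsening abnormalities at Visit 5/EOT will be recorded as AEs". The synopsis and SAP 7.3 say the same, and none of the three makes an exception for LSRs.

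**LSR rule.** Also in Protocol 3.1.2 and the synopsis: "Erythema, edema, erosion/ulceration, scaling/dryness, and scabbing/crusting in the treatment area will be assessed by the PI", on a scale from 0 to 3. The subject scores itching and pain. The AE rule is restrictive: "Only LSRs that require medical intervention (e.g., prescription medication), require withholding or discontinuation of the application of the study drug, or extend 2 cm beyond" (measured from the area treated); reactions of these kinds become AEs. It is followed by "Any LSRs that are not listed above will be recorded as an AE", so the three triggers govern the listed reactions only. SAP 7.2 repeats the three triggers, but without the restricting word *only* and without the sentence on unlisted reactions.

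**Third rule.** Protocol 7.2.3 has the investigator judge laboratory results, examination findings and vital signs for clinical significance: "Any clinically significant results that represent and new or worsening change from Baseline should be recorded as an AE".

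**Analysis.** SAP 8.12.4 says "Findings from the physical exam will be recorded in medical history (from assessment at Screening and Baseline) or as AEs", the latter for Visit 5. Protocol 8.4.2 takes the same approach. AE incidence is listed first among the primary safety endpoints (Protocol 3.2.1, SAP 3.4).

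**The concern.** The five signs that the investigator scores as LSRs (erythema, edema, erosion/ulceration, scaling/dryness, scabbing/crusting) can all be seen when the face is examined. At Visit 5 the same investigator does both assessments on the same skin. A site that finds mild new scaling has one sentence telling it to record an AE, another telling it not to unless a trigger is met, and a third telling it to decide on clinical significance. No passage says which prevails.

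Two kinds of inconsistency can follow. Sites may read the text differently, so part of the AE count would reflect site practice. Visits may also differ: no examination is scheduled at Visits 3 and 4, so the same sign there is an AE only if a trigger is met, while at Visit 5 it may be an AE on sight. In a trial of 36 subjects, a few such entries change the headline percentage.

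**Working it through.** The documents give no AE or LSR rate, so there is no plan figure to reproduce. The check is mainly a comparison of the rules.

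**Step 1: apply each rule to the same finding on the face.**

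| Finding | Examination sentence (3.1.2) | LSR sentence (3.1.2) | Section 7.2.3 |
|---|---|---|---|
| Listed sign, new or worse at Visit 5, no trigger, not clinically significant | AE | not an AE | not an AE |
| Same, judged clinically significant | AE | not an AE | AE |
| Listed sign at Visit 5, trigger met | AE | AE | AE if judged significant |
| Unlisted reaction at Visit 5 | AE | AE | AE if judged significant |
| Listed sign at Visit 3 or 4, no trigger | no examination scheduled | not an AE | no scheduled examination finding |

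The examination and LSR sentences conflict in the first two rows only. Section 7.2.3 sides with one sentence in row 1 and with the other in row 2, so it does not settle the matter.

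**Step 2: check whether timing removes the overlap.** It does not. Visit 5 takes place 3 to 7 days after the final application (Schedule of Events, footnote p). For a completer whose reaction is first seen at Visit 5, dosing has already ended, so the withholding/discontinuation trigger can hardly operate. The LSR rule is at its narrowest at the visit where the examination rule is at its widest.

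**Step 3: check that these entries reach the endpoint.** AEs from first dose to the final study visit are treatment-emergent (Protocol 7.2), and SAP 8.12.2 counts subjects with each treatment-emergent AE. A Visit 5 entry therefore counts.

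**Step 4: size per subject.** Inputs: 36 randomized (Protocol 3.3) at 2:1 (Protocol 5.1.1).
- Nominal arms: 36 × 2/3 = 24 NB01, and 36 − 24 = 12 vehicle.
- One subject with no other AE, counted under one rule and not the other: 1/24 = 4.2 points (NB01), 1/12 = 8.3 points (vehicle), 1/36 = 2.8 points overall.

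**Step 5: illustration on assumed rates.** Let *a* be the share of subjects with some other AE, and *q* the share with a new or worse listed sign on the face at Visit 5 that meets no trigger. Assume the two are independent. Incidence is *a* under the LSR rule and 1 − (1 − *a*)(1 − *q*) under the examination rule, a shift of *q*(1 − *a*).

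| *a* | *q* = 5% | 10% | 20% | 30% |
|---|---|---|---|---|
| 20% | 24% | 28% | 36% | 44% |
| 40% | 43% | 46% | 52% | 58% |

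The shift runs from 0.05 × 0.60 = 3 points to 0.30 × 0.80 = 24 points. The chance that at least one of 24 NB01 subjects is affected is 1 − (1 − *q*(1 − *a*))^24. This runs from 1 − 0.97^24 = 52% to 1 − 0.76^24, which is above 99%. The values of *a* and *q* are assumptions, not document figures.

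**The case against.** The best defence is that the text can be read sensibly as a whole. The LSR sentence is specific and exclusive, the examination sentence is general and covers four body regions, and 7.2.3 filters examination findings by significance. On that reading, listed signs follow the LSR rule and everything else follows 7.2.3. This is a reasonable intention, but neither document states it, and SAP 7.2 leaves out the very word the argument rests on. It is fair to add that, without that word, SAP 7.2 and 7.3 do not strictly contradict each other. The conflict lies in the protocol, and the SAP fails to resolve it.

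The defence is right on several limits:
- Randomization is central and treatment is blinded, so a site's reading applies to both of its arms.
- LSR presence and severity is itself a primary endpoint. SAP 8.12.3 tabulates each LSR by severity, arm and visit, and shows worsening from Screening at Visit 5 by arm.
- SAP 8.12.2 reports AEs by system organ class, preferred term, severity and relationship. No test on AE incidence is planned.

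A reader might infer something stronger: that trivial findings common to both arms would hide a true NB01 excess. Suppose other AEs occur in 30% v 10% (risk ratio 3.0) and *q* = 10% in each arm. Incidence becomes 1 − 0.70 × 0.90 = 37% v 1 − 0.90 × 0.90 = 19%, a ratio of 1.95. But the rates are invented, and the result needs *q* to be equal in both arms. If NB01 itself caused the signs, the examination rule could widen the gap instead. In this example the difference shrinks from 20 to 18 points, a change smaller than one vehicle subject. Any dilution affects the pooled any-AE figure; an excess of another kind keeps its own preferred-term row.

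A reader might also infer that the disputed entries cannot be told apart from other AEs. The preferred-term tables and the Visit 5 LSR scores largely allow it.

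**Conclusion.** The conflict is real and stands in the current protocol text, with 7.2.3 as a third standard and no order of precedence. It is confined to the five listed signs scored by the investigator, in the treatment area, at the Visit 5 examination, when no LSR trigger is met.

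Its consequence is for the level of overall AE incidence and for its consistency across sites and visits. It is not a built-in bias between arms, and the documents do not support saying that an NB01 signal would be lost. The firm figure is 4.2 points per reclassified NB01 subject and 8.3 per vehicle subject, which assumes arms of exactly 24 and 12 and no other AE in that subject. How many subjects are affected cannot be known from the documents; the 3 to 24 point range rests wholly on assumed rates.

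Because this touches the first-listed primary endpoint and is cheap to settle, it should be corrected, but it does not threaten the trial's main safety reading.

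**What to change.** **Wording.** Reconcile Protocol 3.1.2, the synopsis and 7.2.3 with SAP 7.2, 7.3 and 8.12.4. State one LSR rule for when a listed sign in the treatment area is recorded as an AE, to apply whichever assessment finds it and at every visit. State one threshold for all other examination findings; 7.2.3 already contains one. Make SAP 7.2 match the protocol on both the restriction and the unlisted reactions.

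**Data already collected.** Protocol 3.3 describes the 36 subjects as already randomized, so rewording alone may come too late. Before the initial data freeze and the unblinding of the project statistician (SAP 8.3), carry out a blinded review. It should identify AEs that are a listed LSR sign in the treatment area, were first recorded at Visit 5, and have no LSR trigger documented. Check them against the Visit 5 LSR scores and do not rely on onset date alone. State the reference visit, because 7.2.3 compares with Baseline and SAP 8.12.3 with Screening. Then report treatment-emergent AE incidence by arm with and without these events. The figure without them is the one that follows a single rule across sites and visits.

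This review is not a substitute for a table of examination changes, since it captures only one kind of finding.

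**Cost.** A few sentences in each document, a small blinded review and one extra row in the AE summary. The downside is that a few mild findings will appear only in the LSR tables when AEs are counted under the single rule.

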3.1.3. Exploratory Engraftment

Engraftment Assay

Follicular engraftment sampling will be completed via use of Biore® Strips applied across the bridge of the nose extending to either cheek. Skin surface engraftment sampling will be completed via cheek swab.

3.1.4. Exploratory Efficacy

Investigator's Global Assessment

Overall severity of acne will be assessed using a five-point scale where 0=Clear, 1=Almost Clear, 2=Mild, 3=Moderate, and 4=Severe. This is a static morphological scale that refers to a point in time and not a comparison to Baseline (see [Appendix 3](#)).

Acne Lesion Counts

The number of total lesions, inflammatory lesions (papules and pustules), and non-inflammatory lesions (open and closed comedones) on the face (including those present on the nose) will be counted. Counts of nodules and cysts will be reported separately and are not to be included in the inflammatory or non-inflammatory lesion counts.

Acne Quality of Life (QoL) Questionnaire

At each visit, subjects will be asked to complete the Acne QoL Questionnaire to assess subjective improvement of acne (see [Appendix 5](#)).

3.1.5. Exploratory Sebum

At each visit, sebum levels will be assessed for any changes from Screening/Baseline to Weeks 2, 7, and 12.

3.2. Endpoints

3.2.1. Primary Safety Endpoints

The safety endpoints of this study are:

- Incidence (severity and causality) of any local and systemic AEs.
- Number of subjects with presence (and severity) of each LSR and each time point.
- Changes from Screening/Baseline in physical examination findings at Visit 5/EOT.

- Changes from Screening/Baseline in vital signs at Visit 5/EOT.
- Changes from Screening in local CBC at Visit 5/EOT.

3.2.2. Exploratory Engraftment Endpoint

The engraftment endpoint for this study is:

- For skin engraftment assay, absolute and percent change from Screening to follow-ups in Cas5/PanBac and for follicular engraftment assay, the proportion of subjects with “success” at EOT where “success” is defined as a Follicular Biore® sample with “yes” outcome based on recovery of live NB01.

3.2.3. Exploratory Efficacy Endpoints

The efficacy endpoints of this study are:

- Absolute change from Screening at each follow-up visit in IGA score. Percentage of subjects with (a) at least a one-point change in IGA score and (b) percentage of subjects with at least a two-point change in IGA score from Screening at each follow-up visit.
- Absolute and percent change from Screening at each follow-up visit in total, inflammatory, and non-inflammatory lesions.
- Absolute and percent change from Screening to follow-up in Acne QoL.

3.2.4. Exploratory Endpoint

The exploratory endpoint of this study is:

- Absolute and percent change from Screening to follow-up in sebum production.

3.3. Study Design

This is a multicenter, randomized, double-blind, vehicle-controlled Phase 1B study of daily doses of topically-delivered NB01 or vehicle-control in subjects with moderate, non-cyclical facial acne.

Subjects who consent to participate in the study will initiate Screening procedures, during which they will be pre-treated with 5% topical BPO gel once daily (QD) for 5 to 7 days before randomizing into the study. Subjects with modified screening period schedules may be able to apply BPO for more than 7 days; however, this must be pre-approved by the Sponsor’s Medical Monitor.

Thirty six subjects were randomized into the study to receive high-dose NB01 (10^5 CFU/cm²) or vehicle-control.

Subjects will be stratified according to these variables:

- Sex (male/female)
- Age (18-25 years old/26-40 years old)

The study will comprise of subjects with moderate facial acne who will be randomized to one of two treatment arms, either vehicle-control or high-dose NB01.

The study arms consist of vehicle-control control and daily high-dose (10^5 CFU/cm²) NB01, with subjects enrolled at a 2:1 ratio (treatment arm to vehicle-control arm). The PI may employ a dose reduction strategy with approval from the Sponsor's Medical Monitor to reduce/modify dosing based on individual subject's tolerability. Such changes, however, shall not be made without the written approval of the Medical Monitor, see [Section 7.4](#).

Subjects will remain on study through 11 weeks of study treatment.

3.4. Study Treatments

On Day 1, the first study drug dose will be PI-applied approximately 24 hours after the subject has completed their final BPO dose. After Day 1, subjects will continue to apply study drug to the whole face at approximately the same time every evening, for 11 weeks. Subjects will hold all at-home facial washing, shaving, and/or product application on study visit clinic days; once pre-wash procedures have been completed at the study visit, subjects may wash their face at the study clinic.

